#### **D. Disclosing results**

##### **Plan for Neonates Testing Positive for *S. aureus* and disclosure of results:**

The Johns Hopkins Hospital has an active program to identify neonates that are colonized with *S. aureus*. A protocol exists such that colonized neonates are decolonized to reduce the spread of *S. aureus* in the NICU and the risk of infection in individual patients. If a culture collected during the research study grows *S. aureus*, this information will be provided to the clinical team.

##### **Plan for Parents Testing Positive for *S. aureus* and disclosure of follow-up results:**

Upon enrollment, all subjects will be provided a brief structured orientation and education session regarding *S. aureus* by a member of the research team. All patient questions will be answered and educational handouts will be provided with references for additional information. Part of the informed consent will include an understanding that parents will be made aware of their *S. aureus* colonization status. If either or both parents are colonized, parents will be informed that one or both parents are colonized,

but we will not share which parent to protect confidentiality. By participating in the trial, others may also become aware that one of both of the parents are colonized simply by their participation in the trial. We will explain that approximately 30% of healthy adults are colonized with *S. aureus*. We do not take special precautions or treat parents differently that are colonized with *S. aureus*. Additionally, we will enroll both parents even if only one parent is colonized, which will aid in protecting the privacy of participants as care providers will not know if a particular parent is colonized simply based on enrollment in the study, as it might be “the other parent” that is colonized.

Once parents are randomized to an assigned treatment, they will continue to be screened for *S. aureus* colonization throughout the study. The results of subsequent testing will not be made available to the parent. Disclosing subsequent testing results may lead to unmasking of the study. Parents will be informed that these results will not be available until the study is complete and the randomization code is un-blinded for data analysis. Parents will be provided with a means to contact the study team to learn their testing results and/or randomization group.

Parents with discordant culture results should not become aware of each other’s colonization status. To decrease or eliminate guilt issues, the study team will not disclose which parent is colonized and will educate parents on the ubiquity of *S. aureus* and emphasize that parents are only one possible source of transmission.

## **E. Potential Benefits**

There may be no direct benefit to the subjects in this study; however, information obtained in this research may lead to a better understanding of how neonates acquire *S. aureus* in the NICU and whether eradicating colonization in parents reduces neonatal *S. aureus* acquisition and infection.

## **7. Specimen Collection and Laboratory Methods**

### **A. Specimen Collection**

**Swabs will be collected as outlined below:**

#### **Neonates**

Using standardized methodology, four flocked swabs will be obtained from

1. Bilateral nares: by inserting a swab 0.5-1cm into each nares and rotating the swab 3 times (if nares is not available, study team will collect a throat swab instead by inserting a swab in the pharynx and swabbing the region of the tonsils with a quick rotating motion three times on each side).
2. Groin: The groin will be swabbed in a back and forth motion 3 times on each side.
3. Umbilicus: For children who still have an umbilical stump, the base of the umbilical cord will be swabbed in a circular motion 3 times (if there is no umbilical cord, there will be no umbilicus swab).

4. Peri-anal area: The peri-anal area will be swabbed in a circular motion 3 times

### **Parents**

Using standardized methodology, four flocked swabs will be obtained from

1. Bilateral nares: Study staff will collect these by inserting a swab 0.5-1cm into each naris and rotating the swab three times
2. Throat: Study staff will collect this by inserting a swab in the pharynx and swabbing the region of the tonsils with a quick rotating motion three times on each side.
3. Groin: Parents will be instructed by study staff on how to collect these samples. Parents will be able to choose whether they prefer to self-collect the swab or have the study team member collect the swab.
4. Peri-anal: Parents will be instructed by study staff on how to collect these samples. Parents will be able to choose whether they prefer to self-collect the swab or have the study team member collect the swab.

## **B. Laboratory Methods**

### **Processing of cultures collected by the study team**

#### **Parents' Screening Cultures:**

1. An aliquot (10 $\mu$ L) from each culture specimen will be plated on MSSA Select (Bio-Rad Laboratories, Redmond, WA) selective and differential medium to detect *S. aureus*. Presence of mauve colored colonies after 24 hours of incubation will be confirmed as *S. aureus* by Gram's stain and coagulase testing. In parallel, 10 $\mu$ L of each specimen will also be plated on a sheep blood agar plate. Residual specimen (Amies media) will be transferred to cryovials and stored at -70°C. All cultures that grow *S. aureus* will be archived in Tryptic Soy broth with 20% glycerol at -70°C
2. To enhance detection of *S. aureus*, an aliquot (100 $\mu$ L) of medium will be inoculated into Tryptic Soy broth with 6.5% NaCl and incubated overnight for 18-24 hours at 35°C. 10 $\mu$ L of broth will be inoculated onto sheep blood agar and MSSA Select (Bio-Rad Laboratories, Redmond, WA) and processed as described above to detect *S. aureus*. Isolates recovered by this method will be archived in Tryptic Soy broth with 20% glycerol at -70°C.
3. To distinguish methicillin-resistant *S. aureus* (MRSA) and methicillin-susceptible *S. aureus* (MSSA), isolates will be tested on the BD Phoenix Microbial identification system and with other phenotypic testing methods. Screening cultures obtained from parents will not be tested in real-time to distinguish MRSA and MSSA. Parents who are colonized with MRSA will not be identified. There is no standard of care in terms of how to manage parents or visitors that are colonized with MRSA. We do not screen visitors and there is no consensus that colonized visitors should be treated any differently other than following standard precautions (hand washing, covering wounds, etc.).

#### **Neonates' Baseline Colonization Cultures:**

Specimens from neonates will be processed as described in 7.B.2-7.B.3 above (no direct plating, i.e. all specimens will be inoculated into broth before plating).

#### **Follow-up Cultures for both Neonates and Parents:**

Follow-up cultures for both neonates and parents will be processed as described in 7.B.2-7.B.3 above (no direct plating).

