All swabs will receive a study number pre-printed on a label. The SN will not identify the patient's name, medical record number or other identifying information. The SN will be recorded on the informed consent documents and the surveillance swabs. Before sending the swabs, a member of the research team will take a brief "time-out" to reassess that all paperwork is completed, that swabs are appropriately labeled with SN, and that all consent forms and swabs contain the same SN.

Laboratory methods for determining whether a patient has *S. aureus* colonization are described below in Section 7.B. *S. aureus* colonization will be defined as a culture from any anatomic site that grows *S. aureus*.

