**3. Eradication of *S. aureus* colonization in parents following treatment**

**Outcome ascertainment** – Parents will be monitored as described above in section 4.D to monitor *S. aureus* colonization over time. Parents will be tested at baseline, and then every two weeks for the first two months, if available, while neonate remains in the NICU, monthly starting on third month their neonate remains in the NICU, at the time the infant acquires *S. aureus* colonization in the NICU, and at time of discharge from the NICU for a neonate that did not acquire *S. aureus* colonization in the NICU.

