#### **4. Natural history of *S. aureus* colonization in parents receiving placebo**

**Outcome ascertainment** – same as above for parents receiving placebo

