**Table 4: Definition of individual parent and family compliance to treatment**

Individual parent compliance assessment		
Category	Sub-category	Definition
Compliant	Confirmed compliant	seal broken on nasal ointment
	Reported compliant	participants reported use
Non-compliant	Confirmed non-compliant	kits were returned unused
	Reported non-compliant	parent reported non-use
	Presumed non-compliant	parent was lost to follow up without reporting use
Family- level compliance assessment		
Category	Individual 1 compliance	Individual 2 compliance
Compliant	Compliant	Compliant
Partially compliant +	Compliant (SA colonized)	Non-compliant (not SA colonized)
Non-compliant	Compliant (not SA colonized)	Non-compliant (SA colonized)
Non-compliant	Non-compliant	Non-compliant

+partially compliant if *S. aureus* colonized parent is compliant, even if the non-colonized parent was non-compliant

Lastly, within each treatment group, we will use standard survival analysis methods (e.g. Kaplan-Meier survival function curve) to explore the loss of and potential reacquisition of *S. aureus* among the parents, separately for each treatment group. Cox proportional hazards models will be used to describe the association between loss of and reacquisition of *S. aureus* with baseline parent characteristics and treatment.

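### Parents are screened by direct plating plus broth at four sites but followed at interim visits by broth only at three, so some apparent parental loss of S. aureus can come from the change of test

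*Combined protocol and SAP*

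**What the plan says.** Under Parents' Screening Cultures (Section 7.B), step 1 takes 10 µL "from each culture specimen will be plated on MSSA Select (Bio-Rad Laboratories, Redmond, WA) selective and differential medium to detect" S. aureus, with a further 10 µL on sheep blood agar in parallel. Step 2, included to improve detection, takes 100 µL "of medium will be inoculated into Tryptic Soy broth with 6.5% NaCl and incubated overnight for 18-24 hours at 35°C" and then plates 10 µL of the broth. Step 2 is not made conditional on a negative direct plate.

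For later visits the same section says "Follow-up cultures for both neonates and parents will be processed as described in 7.B.2-7.B.3 above (no direct plating", so step 1 is deliberately left out.

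Section 4.C.5 says that "colonization will be defined as a culture from any anatomic site that grows" S. aureus. It sets no limit by culture method, so growth on a direct plate alone makes a parent colonized at baseline.

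Section 4.D and Table 1 list nares, throat, groin and peri-anal swabs at screening. At the interim visits (weeks 2, 4, 6, 8, 12 and so on) they list nares, throat and groin only. The peri-anal swab returns at the final visit.

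Three analyses follow parents from that baseline:
- Eradication (Section 5.B.3): "Parents will be tested at baseline, and then every two weeks for the first two months, if available".
- Natural history in placebo parents (Section 5.B.4), with ascertainment "same as above for parents receiving placebo".
- The Kaplan-Meier and Cox work at the end of Section 9.C "to explore the loss of and potential reacquisition of" S. aureus.

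None of these defines loss, requires the same culture method on both occasions, or restricts the comparison to common sites.

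**The concern.** At baseline a parent has two culture routes and four sites by which to be positive. At an interim visit there is one route and three sites. The baseline test can find everything the interim test can, and more, so the mismatch works one way: towards recording loss when carriage has not changed. A parent positive only at the peri-anal site could also be recorded as lost at week 2 and as having reacquired S. aureus at the final visit, when that site is swabbed again.

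Reducing parental colonization is a secondary hypothesis (Section 3.D), so the eradication result will be read as evidence on how the intervention works. The placebo natural-history outcome is more exposed, because it is a single-arm description with no comparator against which the artefact could cancel.

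**Working it through.** The plan states no figure for this point, so there is none to reproduce. The check sets the procedures side by side and then bounds the size.

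**1. The tests compared** (Sections 4.D and 7.B, Tables 1 and 2)

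| Occasion | Culture route | Sites |
|---|---|---|
| Parent screening | direct plating and broth | nares, throat, groin, peri-anal |
| Parent interim visit | broth only | nares, throat, groin |
| Parent final visit | broth only | nares, throat, groin, peri-anal |
| Neonate baseline and follow-up (study cultures) | broth only | same sites, umbilicus only while the cord is attached |

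The mismatch is confined to parents.

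**2. How common direct-only positives could be at one site.** The documents give no rate. Assume Poisson sampling, λ organisms per 100 µL, v µL plated directly (10, or 20 if the blood agar plate is counted), and growth of every organism plated:

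d = (1 − e^(−λv/100)) · e^(−λ) / (1 − e^(−λ(1+v/100)))

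- As λ approaches 0, d approaches 10/110 = 9.1% or 20/120 = 16.7%.
- At λ = 1, d = 5.2% or 9.5%.
- At λ = 5, d = 0.3% or 0.4%.

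A parent is direct-only only if no screened site is broth-positive. Over several sites the loads add, which lowers d.

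**3. What the method change adds when broth can find the carrier next time.** Hold true carriage unchanged. Apparent loss is the chance of a negative follow-up broth given a positive baseline:

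- either-method baseline: E[(1 − e^(−λ(1+v/100))) e^(−λ)] / E[1 − e^(−λ(1+v/100))]
- broth-only baseline: E[(1 − e^(−λ)) e^(−λ)] / E[1 − e^(−λ)]

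If all carriers have λ = 1, both equal e^(−1) = 36.8%, and the method change adds nothing. With lognormal loads (assumed median 1 to 100 per 100 µL, log-SD 2.3 to 3.5), the either-method baseline adds about 0.05 to 1.4 points. The top of that range is median 1, log-SD 2.3, 20 µL: 18.8% against 17.4%. The bottom is median 100, log-SD 2.3, 10 µL: 1.16% against 1.11%.

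**4. Worst case: broth never detects a direct-only carrier.** Apparent loss = L + (1 − L)d, where L is true loss. With assumed true loss of 20% (placebo) and 60% (treated):

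| d | Placebo | Treated | Difference | Ratio of loss | Ratio of persistence |
|---|---|---|---|---|---|
| 0% | 20.0% | 60.0% | 40.0 | 3.00 | 0.50 |
| 2% | 21.6% | 60.8% | 39.2 | 2.81 | 0.50 |
| 5% | 24.0% | 62.0% | 38.0 | 2.58 | 0.50 |
| 10% | 28.0% | 64.0% | 36.0 | 2.29 | 0.50 |

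The addition is d(1 − L). At d = 5% that is 4 points in placebo and 2 in treated. With equal true loss in both arms the difference stays at 0.

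**5. The peri-anal part.** Replace d by p, the share of screen-positive parents positive only at the peri-anal site. At interim visits that site cannot be positive because it is not swabbed, so the formula in step 4 applies unless another site turns positive. The documents give no p. If it were 2% to 10% (an assumption for illustration), the table in step 4 would apply with p in place of d.

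**The case against.** The strongest reply is that the method change hardly matters. Broth receives 5 to 10 times the volume plated directly and is there to improve detection, so direct-only positives should be uncommon, and nothing in the documents suggests that salt broth misses particular strains. A carrier missed by chance at screening may well be found by broth at the next visit. This stands, and it is why the culture-method part is put at about 0 to 1.4 points. A reader might infer that parental loss is overstated by 2 to 10 points from the method change alone. That would need persistent broth failure, which the documents do not support.

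A reader might also infer that equal spurious loss enters both arms and dilutes the relative effect. It does not enter equally, since the addition d(1 − L) is smaller where true loss is greater. Whether the effect is diluted depends on the measure: the difference and the ratio of loss shrink, while the ratio of persistence does not move.

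Two further objections stand. The plan never says that one negative visit counts as loss, so the artefact arises only under a definition still to be written. And matching the methods does not remove ordinary chance loss: at λ = 1, 36.8% remains with broth at both times. Neither is a reason to leave baseline and follow-up on different tests.

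**Conclusion.** The point holds as a minor one. The plan measures parental colonization with a wider test at screening than at interim visits, in culture route and in sites, and nothing in the outcome definitions or the analysis plan corrects for it.

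The culture-method part is probably small, under the assumed loads and Poisson sampling, and is bounded by d only if broth repeatedly fails. The peri-anal part may be larger, because that site is never sampled at interim visits, but it cannot be sized from the documents.

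It would be wrong to read this as a threat to the main result. Study-collected neonatal cultures are broth-only throughout, concordance uses the strain from the initial parent screening (Section 5.A), and the mismatch is the same in both masked arms, so it cannot create a treatment difference where none exists. What is at stake is the absolute level of loss in each arm, above all in the placebo natural history, together with spurious reacquisition and the difference or ratio of loss between arms.

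**What to change.** Keep eligibility (growth by either method at any site) and the screening strain used for concordance unchanged. For secondary outcomes 3 and 4 and the parental loss and reacquisition analysis, add to the SAP that:

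- baseline colonization is taken from the screening broth culture (step 2);
- it is compared with follow-up only at sites sampled on both occasions: nares, throat and groin at interim visits, all four sites at the final visit;
- parents positive at screening by direct plating alone, or only at the peri-anal site, are counted and reported separately, which would also show the actual shares d and p.

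Matching the broth without matching the sites would leave overall status mismatched at interim visits, so both parts are needed.

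No new specimens are required, because the broth culture is already specified for every parent screening specimen. Section 9.C provides for documenting changes in the analyses before database lock and unmasking. The costs are a few parents lost from the interim parental analyses and the need to hold screening results by method and site. Section 7.B describes archiving isolates but names no such data field, so its availability should be confirmed first.

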#### **Processing of cultures obtained during routine clinical care**

1. As usual, all cultures sent to the Johns Hopkins Microbiology laboratory will be processed according to Clinical and Laboratory Standards Institute guidelines. All clinical cultures that grow *S. aureus* will be archived in Tryptic Soy broth with 20% glycerol at -70°C.

#### ***S. aureus* strain typing:**

1. Strains of *S. aureus* will be compared using pulsed-field gel electrophoresis (PFGE) analysis. DNA will be extracted by standard methods and the restriction enzyme digested using *Sma*1. A *Staphylococcus aureus* subspecies NCTC 8325 will be used as a control strain with a molecular weight ladder at the beginning and end of each gel. Control isolates, including all USA PFGE strain types, will be used for comparison. Using 1% pulsed-field certified agarose gel (BioRad Laboratories, Hercules, CA) electrophoresis will be performed on the CHEF-DR III (BioRad Laboratories, Hercules, CA) with 0.5X TBE buffer at 14°C. The gels will be stained with ethidium bromide and scanned using a molecular analysis fingerprinting software (Fingerprinting II Version 3.0; BioRad Laboratories, Hercules, CA). If PFGE using standard enzymes was unable to yield an interpretable fingerprint, PFGE was then performed using an alternative method utilizing Achromopeptidase (Wako Bioproducts, Richmond, VA) as the lysis enzyme in order to obtain an interpretable fingerprint. Gel images will be stored and within and between run comparisons will be performed for each group of tested isolates. Isolates will be considered related if their patterns have ≤3 band differences. Isolates with >3 band differences will be considered epidemiologically different strain types.
2. Alternative *S. aureus* strain typing method: Because some *S. aureus* strains are genetically similar by PFGE, such as strain USA300, validation of highly prevalent and concordant strains will be carried out using a separate assay such as a PCR assay coupled with electrospray ionization-mass spectrometry (PCR/ESI-MS), whole genome or next generation sequencing, or multi-locus sequence typing. Isolates with no band differences will be considered identical, but those with 1-3 band differences will be considered for additional testing based on strain prevalence.
3. If strains could not be distinguished by PFGE analysis, multi-locus sequence typing (MLST) will be performed using whole genome sequencing. After DNA extraction, a sequence library will be generated using the Nextera DNA Library Preparation Kit and sequenced by Miseq (Illumina Inc, San Diego, CA). Sequenced fragments will be assembled using SPAdes and aligned to reference

*S. aureus* genome with Pavian (Johns Hopkins University, Baltimore, MD) for quality assessment. Strain type will be assigned by The Bacterial Analysis Pipeline (Illumina Inc, San Diego, CA) based on the alleles of seven housekeeping genes, including arcc, aroe, glpf, gmk, pta, tpi, and yqil. Two isolates will be considered concordant if both had identical alleles for all seven genes.

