## **5. Primary and Secondary Endpoints and Outcomes**

### **A. Primary: Primary outcome is neonatal acquisition of *S. aureus* strain that is concordant to parental *S. aureus* strain as determined by periodic surveillance cultures or a culture collected during routine clinical care that grows *S. aureus*.**

Acquisition will be defined as meeting two criteria:

- 1) A neonate who had baseline surveillance cultures that were negative for *S. aureus*
- 2) A neonate who has a subsequent surveillance culture or culture collected during routine clinical care that grows *S. aureus*.

Concordant strains must meet the following criteria:

- 1) Strains that are related using pulsed-field gel electrophoresis (PFGE) analysis, as described below. Isolates will be considered related if their patterns have  $\leq 3$  band differences. Isolates with  $>3$  band differences will be considered epidemiologically different strain types. A neonate who has a subsequent surveillance culture or culture collected during routine clinical care that grows *S. aureus*.
- 2) Alternative typing methods will be used to further discriminate highly prevalent strains or those that are not typable by PFGE.
- 3) The same strain from the initial parent screening is identified from the neonate.

**Primary outcome ascertainment** – We will measure each neonate's baseline *S. aureus* colonization status at the time of study enrollment. As described above, neonates will then have swabs collected weekly after enrollment and at time of discharge from multiple anatomic sites by a study team member. We also will use data from cultures collecting during routine clinical care in the NICU. These cultures include cultures of nasal swabs collected every Tuesday as part of an active *S. aureus* surveillance program and other cultures collected during routine clinical care (e.g. blood cultures, respiratory cultures, wound cultures, etc.). Cultures collected by the study team and cultures collected during routine clinical care will both be used to identify *S. aureus* acquisition in neonates. Of note, nasal surveillance swabs collected as part of the hospital surveillance program are plated on selective media plates to detect *S. aureus* colonization, as previously reported [1].

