## **9. Statistical Analysis Plan**

### **A. Sample size and power estimates:**

The primary outcome will be time to concordant *S. aureus*-colonization. Time to concordant *S. aureus* colonization will be expressed using an indicator variable for concordant colonization and time to concordant colonization. The a priori assumed

control group concordant colonization rate is 10% and power calculations are based on the unadjusted Cox proportional hazards model where the primary covariate is the treatment group indicator. In time to event analyses, power is driven by the number of events; i.e. number of concordant colonizations. Given our assumed control group concordant colonization rate of 10%, 38 events are required to detect a 60 percent reduction in the hazard of concordant colonization (Hazard Ratio: HR 0.4) in the intervention group with 80% power and Type I error rate of 5%. The 38 events includes a roughly 2% inflation for pre-planned interim analyses (see Section 9.B). Given that we expect 5% of the parent-neonate pairs will be non-singleton births, we increased the number of required events to 40 to account for the possible clustering of concordant colonization among non-singleton neonates. Some neonates may test positive at baseline for *S. aureus* after randomization and will not be eligible for the analysis of the primary outcome. Similarly, if one neonate from a multiple gestation birth is positive for *S. aureus* at baseline and another neonate is not, then the negative infant will be eligible. Eligible parent-neonate pairs will be assigned to either treatment or control as a unit until 40 events are confirmed. Prior to the start of the study, given our *a priori* assumption of a 10% concordant colonization rate in the control group and a HR of 0.40, we anticipated recruiting 400 parent-neonate pairs to achieve the required 40 concordant colonizations. With 400 parent-neonate pairs, we have roughly 80% power to detect an absolute risk difference of at least 7% for the secondary analysis of the indicator of concordant colonization within 90 days after randomization.

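### Sections 5.A and 7.B give inconsistent rules for calling strains concordant, and the only stated rule for a second assay reduces a whole-genome sequence to seven genes.

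*Combined protocol and SAP*

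**What the plan says.** Section 5.A defines the primary event as acquisition of a strain concordant with the parent's. PFGE patterns must differ by no more than three bands, and the reference is the parent's screening isolate: "The same strain from the initial parent screening is identified from the neonate". On second assays it says: "Alternative typing methods will be used to further discriminate highly prevalent strains or those that are not typable by PFGE".

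Section 7.B (strain typing) repeats the three-band rule in item 1 and adds an alternative lysis enzyme for isolates that give no readable fingerprint. Item 2 notes that some "strains are genetically similar by PFGE, such as strain USA300", and promises that "validation of highly prevalent and concordant strains will be carried out using a separate assay". The examples it lists are PCR/ESI-MS, whole-genome or next-generation sequencing, and MLST. Its next sentence reads: "Isolates with no band differences will be considered identical, but those with 1-3 band differences will be considered for additional testing", with the choice to depend on strain prevalence. Item 3 then says: "If strains could not be distinguished by PFGE analysis, multi-locus sequence typing (MLST) will be performed using whole genome sequencing". The sequence is used to assign a type from seven housekeeping genes, and the decision rule is "Two isolates will be considered concordant if both had identical alleles for all seven genes".

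Section 9.C plans no sensitivity analysis on the concordance definition.

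**The concern.** The texts disagree on two matters. The first is whether a zero-band pair in a highly prevalent strain gets a second assay. The second is what sends a pair to MLST: failure of PFGE to separate two strains (7.B item 3), or failure of PFGE to type an isolate (5.A). No prevalence threshold, order of assays or rule for conflicting results is given.

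The one stated decision rule also works against its purpose. Two isolates that agree across the genome agree at the seven genes, but the reverse need not hold. Seven-gene identity therefore cannot discriminate more finely than a genome-wide comparison of the same sequences, and it may discriminate less.

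Sections 2.B and 6.D accept that neonates can acquire *S. aureus* from sources other than parents. A neonate who acquires a strain elsewhere that a parent also happens to carry, and whose pair passes the typing rule, becomes a primary event outside the reach of the intervention. Under Section 9.B it also counts toward the looks at 20, 30 and 40 events.

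**Working it through.** **Step 1. Set the typing rules side by side.**

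| Pair | 5.A | 7.B item 2 | 7.B item 3 |
|---|---|---|---|
| More than 3 bands | Different | Not addressed | Not reached |
| 1–3 bands | Related; second method if highly prevalent | Further testing considered, by prevalence | Unclear |
| 0 bands, highly prevalent strain | Second method | Validated (one sentence); identical (the next) | Seven-gene rule, if the trigger means the same pattern |
| Untypable by PFGE | Second method | Not addressed | Seven-gene rule, if the trigger means untypable |

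For an untypable isolate the seven-gene rule decides concordance alone. For a typable pair within three bands, PFGE has already called it related. The seven-gene step can then only remove the match, and only if one of seven genes differs.

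**Step 2. Reproduce the planned event number (Section 9.A).** Inputs: HR 0.40, 80% power, two-sided 5%, equal allocation.

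Events = (1.960 + 0.842)² / (0.25 × (ln 0.40)²) = 37.4. With the stated 2% interim inflation, 37.4 × 1.02 = 38.1. The plan's 38 is reproduced; it then becomes 40 for multiple births.

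**Step 3. Dilution.** Let q be the share of control-arm concordant events that are chance matches, with HR 1. The documents give no value, so q is an assumption.

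- Observed HR = q + (1 − q) × 0.40
- Single-analysis power at 40 events = Φ(√(40/4) × |ln HR| − 1.960). For q = 10%: 3.162 × 0.777 − 1.960 = 0.496, so power is 69.0%.
- Power with the planned looks: simulation with boundaries −2.74, −2.36 and −2.03 at 20, 30 and 40 events, and information equal to events divided by 4 as in Section 9.B. Clustering of multiples is ignored.
- Chance matches among all events, for rare events and equal arms = 2q / (1 + observed HR)

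| q | Observed HR | Power, single analysis | Power, planned looks | Events for 80% power (no interim inflation) | Chance matches among 40 events |
|---|---|---|---|---|---|
| 0 | 0.40 | 82.6% | 82% | 38 | 0 |
| 5% | 0.43 | 76.1% | 75% | 45 | 2.8 |
| 10% | 0.46 | 69.0% | 68% | 53 | 5.5 |
| 20% | 0.52 | 54.3% | 53% | 74 | 10.5 |

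**Step 4. Type I error.** If treatment has no effect, true and chance events both have HR 1, so the mixture does too. The simulated one-sided rejection rate under the null is 2.5%. The cost is power, not false positives.

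**The case against.** A reader might infer that zero-band matches in common strains are accepted without testing. The documents do not establish this. The sentence just before the zero-band statement promises a separate assay for highly prevalent, concordant strains, and 5.A makes no zero-band exception. What stands is a contradiction to reconcile.

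A reader might also infer that the seven-gene rule creates concordance for every pair PFGE leaves unresolved. It does not: for typable pairs it can only take a match away. It decides alone only for untypable isolates, and item 1 already tries to reduce their number with a second lysis method.

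A third temptation is to derive q from the documents: take the figure of up to 40% acquisition in Section 2.B, subtract the 10% concordant rate in 9.A, and multiply the remaining 30% by the square of an assumed lineage frequency of 20–30%. That gives 1.2 to 2.7 points, and q of 1.2/11.2 = 11% to 2.7/12.7 = 21%. This is not supported. The 40% is an upper bound for neonates in their first two months and is not tied to this trial. The lineage frequency has no source in the documents. The product also ignores the exclusion of pairs differing by more than three bands. If only 10% of comparisons were untypable (also an assumption), the seven-gene rule acting alone would add 0.12 to 0.27 points. That makes q about 1–3%, the HR about 0.41–0.42, and single-analysis power about 79–81%.

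Two more points have force. The planned HR of 0.40 may already refer to the endpoint as defined, chance matches included; treating it as the effect on true transmission is an assumption. Sequencing is also among the validation options in item 2, but no decision threshold goes with it. Finally, any acquisition regardless of strain is a planned secondary outcome and does not depend on typing, but for that reason it cannot test the typing rule.

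**Conclusion.** The point holds in a limited form. The typing rules for the primary endpoint are inconsistent between 5.A and 7.B and within 7.B item 2. The only stated rule for a second assay discards most of the sequence generated to apply it. No planned analysis shows how much the result depends on the concordance definition.

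The effect on power is conditional. If true transmission has an HR of 0.40 and chance matches have an HR of 1 in both arms, even q = 5% costs about 7 percentage points (82% to 75%), and q = 20% costs about 29 (82% to 53%). The documents neither give q nor show that chance matches are common, so no row of the table should be read as the expected loss. The risk is a missed effect, not a spurious one. A correction is worth making because the definition determines both the primary result and the timing of every look, and the remedy is inexpensive.

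**What to change.** 1. Reconcile 5.A with 7.B items 2 and 3 in one ordered typing rule. It should define a highly prevalent strain, say whether zero-band pairs in such strains get the second assay, state what sends a pair to sequencing, and say which result prevails when assays disagree.
2. Wherever sequences are generated, judge concordance by a genome-wide distance (core-genome SNPs or cgMLST) instead of seven-gene identity, with the threshold fixed before unmasking.
3. Add to 9.C a sensitivity analysis of the primary outcome in which pairs resolved only by seven-gene identity are not counted as events.
4. Report the background match rate: compare neonatal isolates with the screening isolates of other families at the same site. This would give the trial's own evidence on how often chance matches occur.

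The cost is wording, some bioinformatics and analysis work, and possibly a slightly slower event count, because the events that trigger the looks would be defined more strictly. Sequences exist only for isolates sent to sequencing. Sequencing further zero-band pairs is optional; 7.B archives the isolates that grow *S. aureus*, so it remains possible.
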